8.0 TRIAL PROCEDURES

8.1.1 Registration Procedures

Eligible patients will be entered on the study centrally at the clinical trials office of the Karmanos Cancer Center/Wayne State University, by, the Study Coordinator (or a designated study coordinator). All sites should call the Study Coordinator) after initiating screening.

An eligibility check list will be generated by the Study team at Karmanos Cancer Institute. This eligibility check list has to be completed by each site and signed by the responsible investigator. Once this is received by Study Coordinator and confirmed by him/her, the patient will be registered. A registration confirmation will be sent to the site (sites other than Karmanos Cancer Institute).

Once registration has occurred patient has to be treated within 5 days. If patient does not start therapy within 5 days of registration, the reasons for delay should be communicated to the Principal Investigator. He will then decide if the patient can continue on study therapy.

8.1.2 Informed Consent

The Investigator must obtain documented consent from each potential subject prior to participating in a clinical trial and conducting trial specific procedures.

The informed consent will adhere to individual Institutional Review Board requirements, applicable laws and regulations.

8.1.3 Disease Details

The known sites of metastases at the time of diagnosis and study entry will be recorded. The number of cycles of platinum based chemotherapy received and the date of the last cycle of chemotherapy should be recorded.

Details of any radiation administered for the management of SCLC will be recorded. This will include site radiated, dose and dates.

8.1.4 Clinical Procedures/Assessments

8.1.4.1 Adverse Event (AE) Monitoring

The investigator or qualified designee will assess each subject to evaluate for potential new or worsening AEs as specified in the Trial Flow Chart and more frequently if clinically indicated. Adverse experiences will be graded and recorded throughout the study and during the follow-up period according to NCI CTCAE Version 4.0 (see Section 15.2). Toxicities will be characterized in terms regarding seriousness, causality, toxicity grading, and action taken with regard to trial treatment.

All AEs of unknown etiology associated with MK-3475 exposure should be evaluated to determine if it is possibly an event of clinical interest (ECI) of a potentially immunologic etiology (irAE) (See Section 5.4.1.1)

Please refer to section 7.2 for detailed information regarding the assessment and recording of AEs.

8.1.4.2 Tumor Imaging and Assessment of Disease

Patients will undergo scans to assess the status of the cancer within 3 weeks before the first dose of MK-3475. All known areas of metastases should be imaged. Patients will undergo restaging scans every 2 cycles for the first 6 cycles. Subsequently they can be done as often as necessary, but should be done at least every 4 cycles.

The treating physician will decide which scans need to be done to appropriately assess the status of the cancer.

8.1.4.3 Laboratory Procedures/Assessments

Details regarding specific laboratory procedures/assessments to be performed in this trial are provided below.

Table 8 Laboratory Tests

Hematology	Chemistry	Urinalysis (only at baseline)	Other
Hematocrit	Albumin	Blood	Serum β -human chorionic gonadotropin†
Hemoglobin	Alkaline phosphatase	Glucose	(β -hCG)†
Platelet count	Alanine aminotransferase (ALT)	Protein	Total triiodothyronine (T3) α
WBC (total and differential)	Aspartate aminotransferase (AST)	Specific gravity	Free tyroxine (T4) α
Red Blood Cell Count	Creatinine	Microscopic exam (If abnormal)	Thyroid stimulating hormone (TSH) α
Absolute Neutrophil Count	Carbon Dioxide ‡ (CO₂ or biocarbonate)	results are noted	
	Calcium	Urine pregnancy test †	
	Chloride		Blood for correlative studies
	Glucose		
	Potassium		
	Sodium		
	Total Bilirubin		
	Direct Bilirubin (If total bilirubin is elevated above the upper limit of normal)		
	Total protein		
	Blood Urea Nitrogen		
† Perform on women of childbearing potential only. If urine pregnancy results cannot be confirmed as negative, a serum pregnancy test will be required. This is needed only at baseline ‡ If considered standard of care in your region. α These tests are to be conducted at baseline. Once the patient is on trial therapy tests to be conducted at least every 4 cycles.			

Laboratory tests for screening or entry into the Second Course Phase should be performed within 14 days prior to the first dose of treatment. After Cycle 1, pre-dose laboratory procedures can be conducted up to 48 hours prior to dosing. Results must be reviewed by the investigator or qualified designee and found to be acceptable prior to each dose of trial treatment.

8.1.5 Withdrawal/Discontinuation

When a subject discontinues/withdraws prior to trial completion, all applicable activities scheduled for the final trial visit should be performed at the time of discontinuation. Any adverse events which are present at the time of discontinuation/withdrawal should be followed. Subjects who a) attain a CR or b) complete 24 months of treatment with MK-3475 may discontinue treatment with the option of restarting treatment (see section 8.1.6). After discontinuing treatment following assessment of CR, these subjects should return to the site for a Safety Follow-up Visit (described in Section 8.1.6.1).

8.1.6 Visit Requirements/Safety Follow Up Visit/Retreatment

Visit requirements are outlined in Section 7.0 - Trial Flow Chart. Specific procedure-related details are provided above in Section 8.1 - Trial Procedures.

It is recognized that the safety follow up visit maybe difficult to accomplish in patients with extensive stage small cell lung cancer. However, every effort should be made to conduct a Safety Follow-Up Visit approximately 30 days after the last dose of trial treatment or before the initiation of a new anti-cancer treatment, whichever comes first. All AEs that occur prior to the Safety Follow-Up Visit should be recorded. Subjects with an AE of Grade > 1 will be followed until the resolution of the AE to Grade 0-1 or until the beginning of a new anti-neoplastic therapy, whichever occurs first.

8.1.6.1 Follow-up Visits

Subjects who discontinue trial treatment for a reason other than disease progression will move into the Follow-Up Phase and should be assessed every 12 weeks by radiologic imaging to monitor disease status. Every effort should be made to collect information regarding disease status until the start of new anti-neoplastic therapy, disease progression, death, end of the study or if the subject begins retreatment with MK-3475 as detailed in Section 8.1.6.1.2

Subjects who are eligible to receive retreatment with MK-3475 according to the criteria in Section 8.1.6.1.2 will move from the follow-up phase to the Second Course Phase when they experience disease progression.

8.1.6.1.1 Survival Follow-up

Once a subject experiences confirmed disease progression according to modified response criteria or starts a new anti-cancer therapy, the subject moves into the survival follow-up phase and should be contacted by telephone every 12 weeks to assess for survival status until death, withdrawal of consent, or the end of the study, whichever occurs first.

8.1.6.1.2 Retreatment

Patients who have disease progression following completion of 2 years of therapy with MK-3475 can be re-treated with this drug if the patient meets all eligibility criteria as in Section 5.0 except for the criteria of stable or responding disease following chemotherapy.

The schedule of study activities will be according to the study flow chart Section 6.0.

8.2 Assessing and Recording Adverse Events

An adverse event is defined as any untoward medical occurrence in a patient or clinical investigation subject administered a pharmaceutical product and which does not necessarily have to have a causal relationship with this treatment. An adverse event can therefore be any unfavorable and unintended sign (including an abnormal laboratory finding, for example), symptom, or disease temporally associated with the use of a medicinal product or protocol-specified procedure, whether or not considered related to the medicinal product or protocol-specified procedure. Any worsening (i.e., any clinically significant adverse change in frequency and/or intensity) of a preexisting condition that is temporally associated with the use of MK-3475, is also an adverse event.

Adverse events may occur during the course of the use of MK-3475 from overdose (whether accidental or intentional), from abuse and from withdrawal.

All adverse events will be recorded from the time the patient starts therapy with the study drug through 30 days following cessation of treatment and at each examination on the Adverse Event case report forms/worksheets.

Merck or Principal Investigator will also forward to individual sites relevant SAE reports occurring on MK-3475. These should be forwarded to appropriate regulatory authorities according to local rules and regulations.

8.2.1 Definition of an Overdose for This Protocol and Reporting of Overdose to the Sponsor and to Merck

For purposes of this trial, an overdose will be defined as any dose exceeding the prescribed dose for MK-3475 by 20% over the prescribed dose. No specific information is available on the treatment of overdose of MK-3475. In the event of overdose, MK-3475 should be discontinued and the subject should be observed closely for signs of toxicity. Appropriate supportive treatment should be provided if clinically indicated.

If an adverse event(s) is associated with (“results from”) the overdose of MK-3475, the adverse event(s) is reported as a serious adverse event, even if no other seriousness criteria are met.

If a dose of MK-3475 meeting the protocol definition of overdose is taken without any associated clinical symptoms or abnormal laboratory results, the overdose is reported as a non-serious Event of Clinical Interest (ECI), using the terminology “accidental or intentional overdose without adverse effect.”

All reports of overdose with and without an adverse event must be reported within 24 hours to the Principal Investigator and within 2 working days hours to Merck Global Safety. (Attn: Worldwide Product Safety; [contact])

8.2.2 Reporting of Pregnancy and Lactation to the Principal Investigator and to Merck

Although pregnancy and lactation are not considered adverse events, it is the responsibility of investigators or their designees to report any pregnancy or lactation in a subject (spontaneously reported to them), including the pregnancy of a male subject's female partner that occurs during the trial or within 120 days of completing the trial, or 30 days following cessation of treatment if the subject initiates new anticancer therapy, whichever is earlier. All subjects and female partners of male subjects who become pregnant must be followed to the completion/termination of the pregnancy. Pregnancy outcomes of spontaneous abortion, missed abortion, benign hydatidiform mole, blighted ovum, fetal death, intrauterine death, miscarriage and stillbirth must be reported as serious events (Important Medical Events). If the pregnancy continues to term, the outcome (health of infant) must also be reported.

Such events must be reported within 24 hours to the Study Coordinator and within 2 working days to Merck Global Safety. (Attn: Worldwide Product Safety; [contact])

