As of 26-Jul-2013, there have been 789 patients treated in a phase I trial (PN001) with MK-3475 as a 30-minute IV infusion. Of these 789 patients, preliminary data are available from 479 patients. Based upon this safety database consisting of patients treated up to 10 mg/kg once every two to three weeks, MK-3475 has been generally well-tolerated at doses up to 10 mg/kg every other week without DLTs. One (0.002%) patient assayed to date had samples confirmed positive for ADA, but no impact on safety has been observed. Five other clinical studies (PN002, PN006, PN010, PN011, and PN012) are ongoing however preliminary data analyses are not yet available.

MK-3475 PK results have been obtained from phase I trial following the first dose at 1, 3 and 10 mg/kg IV of MK-3475 administered to 17 patients with solid tumors. Exposure to MK-3475 is approximately linear in the dose range of clinical relevance (1-10 mg/kg). The observed pharmacokinetic profile of MK-3475 was typical of other IgG mAbs with a half-life ($t_{1/2}$) of approximately 2 to 3 weeks. There was no indication of dose dependency of half-life in the 3 dose groups and a dose related increase in exposure was observed from 1 to 10 mg/kg. The long half-life supports a dosing interval of every 2 or 3 weeks. Exposure obtained with sparse sampling after dosing melanoma and non-small cell lung cancer (NSCLC) patients at 2 and 10 mg/kg, every 2 or 3 weeks, is consistent with this profile.

Durable objective responses have been reported in patients with melanoma and NSCLC (15, 16). Adverse events have generally been manageable and infrequently require discontinuation of MK-3475 treatment. MK-3475 phase I trial enrolled 207 patients with NSCLC who experienced progression of cancer after previous systemic therapy. The preliminary objective response rate (ORR) by RECIST v1.1 is 23% (95% CI 16%, 30%) in patients with tumors deemed to be PD-L1 positive and 9% (95% CI 2%, 23%) in patients with tumors that were PD-L1 negative, for an overall response rate of about 17%. The median response duration is 31 weeks.

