5.0 ELIGIBILITY

5.1 Inclusion Criteria

1. Patients with extensive stage SCLC who have completed at least 4 cycles of platinum (carboplatin/cisplatin) and etoposide chemotherapy as their first line therapy and have responding or stable disease to this therapy are eligible for this study. Patients who received platinum/etoposide previously for SCLC and it was repeated for recurrence will not be eligible.
2. Patients should be willing and able to provide written informed consent for the trial.
3. Be ≥ 18 years of age on day of signing informed consent.
4. Have a performance status of 0 or 1 on the ECOG Performance Scale.
5. Demonstrate adequate organ function as defined in Table 1, all screening labs should be performed within 14 days of treatment initiation.

Table 1 Adequate Organ Function Laboratory Values

System	Laboratory Value
Hematological	
Absolute neutrophil count (ANC)	≥1,500 /mcL
Platelets	≥100,000 / mcL
Hemoglobin	≥9 g/dL or ≥5.6 mmol/L
Renal	
Serum creatinine OR Measured or calculated ^a creatinine clearance (GFR can also be used in place of creatinine or CrCl)	≤1.5 X upper limit of normal (ULN) OR ≥45 mL/min for subject with creatinine levels > 1.5 X institutional ULN
Hepatic	
Serum total bilirubin	≤ 1.5 X ULN OR Direct bilirubin ≤ ULN for subjects with total bilirubin levels > 1.5 ULN
AST (SGOT) and ALT (SGPT)	≤ 2.5 X ULN OR ≤ 5 X ULN for subjects with liver metastases
^a Creatinine clearance should be calculated per institutional standard.	

6. Female subject of childbearing potential should have a negative urine or serum pregnancy within 1 week prior to receiving the first dose of study medication. If the urine test is positive or cannot be confirmed as negative, a serum pregnancy test will be required.
7. Female subjects of childbearing potential should be willing to use 2 methods of birth control or be surgically sterile, or abstain from heterosexual activity for the course of the study through 120 days after the last dose of study medication (Reference Section 5.7.2). Subjects of childbearing potential are those who have not been surgically sterilized or have not been free from menses for > 1 year.
8. Male subjects should agree to use an adequate method of contraception starting with the first dose of study therapy through 120 days after the last dose of study therapy.

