6.4 Contraception/Pregnancy/Nursing

6.4.1 Contraception

MK-3475 may have adverse effects on a fetus in utero. Furthermore, it is not known if MK-3475 has transient adverse effects on the composition of sperm. Non-pregnant, non-breast-feeding women may be enrolled if they are willing to use 2 methods of birth control or are considered highly unlikely to conceive. Highly unlikely to conceive is defined as 1) surgically sterilized, or 2) postmenopausal (a woman who is \geq 45 years of age and has not had menses for greater than 1 year will be considered postmenopausal), or 3) not heterosexually active for the duration of the study. The two birth control methods can be either two barrier methods or a barrier method plus a hormonal method to prevent pregnancy. Subjects should start using birth control from study Visit 1 throughout the study period up to 120 days after the last dose of study therapy.

The following are considered adequate barrier methods of contraception: diaphragm, condom (by the partner), copper intrauterine device, sponge, or spermicide. Appropriate hormonal contraceptives will include any registered and marketed contraceptive agent that contains an estrogen and/or a progestational agent (including oral, subcutaneous, intrauterine, or intramuscular agents).

Subjects should be informed that taking the study medication may involve unknown risks to the fetus (unborn baby) if pregnancy were to occur during the study. In order to participate in the study they must adhere to the contraception requirement (described above) for the duration of the study and during the follow-up period defined in section 7.2.2-Reporting of Pregnancy and Lactation to the Sponsor and to Merck. If there is any question that a subject will not reliably comply with the requirements for contraception, that subject should not be entered into the study.

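### Section 8.2.2 can be read to end pregnancy reporting 30 days after treatment stops once new anticancer therapy starts, short of the protocol's own 120-day risk period

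*Combined protocol and SAP*

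**What the plan says.** Section 8.2.2 obliges investigators to report any pregnancy or lactation that a subject tells them about, including pregnancy in a male subject's partner. Each pregnancy must be followed to its end. The duty covers pregnancies during the trial, and later ones only if they occur "within 120 days of completing the trial, or 30 days following cessation of treatment if the subject initiates new anticancer therapy, whichever is earlier".

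The other passages on pregnancy risk count 120 days from the last dose:

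- Section 5.1 item 7 (women): "through 120 days after the last dose of study medication".
- Section 5.1 item 8 (men): "starting with the first dose of study therapy through 120 days after the last dose of study therapy".
- Section 5.2 item 12 excludes anyone who expects to conceive or father a child up to the same 120-day point.
- Section 6.4.1 requires birth control "throughout the study period up to 120 days after the last dose of study therapy".

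None of these is shortened when another cancer treatment begins. Section 6.4.1 gives the reason for caution: "MK-3475 may have adverse effects on a fetus in utero". It later tells subjects to adhere to the contraception requirement "for the duration of the study and during the follow-up period defined in section 7.2.2". Section 7 of the current document holds only the flow chart, and the title printed beside that number is essentially that of 8.2.2.

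Section 4.2.1 (MK-3475) reports a half-life "of approximately 2 to 3 weeks".

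**The concern.** Starting another cancer drug does not remove a long-lived antibody. The event that triggers the short branch therefore has no bearing on how long a pregnancy may be exposed to MK-3475. The documents give no reason for the shorter limit.

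The stake is safety information. The protocol regards the drug as possibly harmful to a fetus and says its effect on sperm is unknown, so each exposed pregnancy is worth recording and following. Pregnancy tests are required only at baseline (Section 7.1 and Table 8), and 8.2.2 relies on subjects volunteering the information. The wording of the duty is thus the main thing that determines whether a later pregnancy is recorded.

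**Working it through.** **Inputs.** Half-life 14 to 21 days (Section 4.2.1, MK-3475). Short reporting limit 30 days after cessation (8.2.2). Contraception period 120 days after the last dose (5.1, 6.4.1). Dosing interval 21 days (Table 2). The documents state no half-life count or residual fraction, so there is no plan figure to reproduce.

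**Formulas.** Half-lives elapsed = days / half-life. Fraction remaining = 2^(−days / half-life), which assumes simple exponential decay from the last dose. Gap = 120 − day on which the reporting duty ends.

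**When the duty ends.** Section 8.2.2 dates the limit from cessation of treatment, which is not defined. If cessation is the last dose, the duty ends on day 30. If it is the decision to stop, taken up to one cycle later (assumption), it ends by day 30 + 21 = 51.

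| Days after last dose | Half-life 14 d | Half-life 21 d |
|---|---|---|
| 30 | 30/14 = 2.14 half-lives, 23% left | 30/21 = 1.43 half-lives, 37% left |
| 51 | 51/14 = 3.64 half-lives, 8.0% left | 51/21 = 2.43 half-lives, 18.6% left |
| 120 | 120/14 = 8.57 half-lives, 0.3% left | 120/21 = 5.71 half-lives, 1.9% left |

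Gap: 120 − 30 = 90 days, or 120 − 51 = 69 days.

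**Does another passage close the gap?**

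- Section 6.4.2 covers a female subject's pregnancy only while she is on treatment. Its sentence on partner pregnancy has no time limit of its own but refers to 7.2.2, and so back to 8.2.2.
- The general window for serious adverse events in 8.2.3.1 ends at 90 days or at new anticancer therapy, whichever comes first, so it closes on the same trigger.
- The open-ended route in 8.2.3.1 needs a serious event that comes to the investigator's attention and is judged related to MK-3475. An uncomplicated exposed pregnancy does not qualify.

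**Starting points.** The 120-day limb of 8.2.2 runs from completion of the trial, while the contraception period runs from the last dose. The two 120-day figures therefore do not describe the same interval.

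**The case against.** The strongest reply is that 8.2.2 also covers pregnancies during the trial, and that the earlier-of clause chooses only between the two later limits. Under 8.1.6.1.1, a subject who starts new therapy moves into telephone survival follow-up. If that phase counts as the trial, a pregnancy on days 31 to 120 is still reportable. This reading is possible, and it is why the point says the section can be read to end the duty, not that it must. But Section 6.5 describes subjects who stop for listed reasons as discontinued from the trial, which points the other way. And if survival follow-up counts, the 30-day branch would almost never operate. Either reading justifies clarifying the text.

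A second reply is that ending collection at new therapy matches the rule for serious events, and that later reports would be confounded by the new drug. Confounding is a real drawback. It limits how a report is interpreted, but it is not a reason to leave the report out.

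Three stronger readings are tempting and not supported:

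- *That exposed pregnancies will go unreported.* The text removes a duty; it does not forbid a report. A pregnancy that occurs by day 30 and is found later is still inside the window, and a drug-related serious event such as a congenital anomaly is reportable at any time.
- *That the short branch will often apply because the planning median PFS is 2 to 3 months.* The documents give no rate or timing for subsequent therapy.
- *That the protocol sets a 30-day contraception period.* No passage says so. That reading comes only from following an outdated section number into a reporting rule, while the same sentence of 6.4.1 refers back to the requirement already described, which is 120 days.

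**Conclusion.** The mismatch stands. On a natural reading, 8.2.2 ends the duty to report and follow subject and partner pregnancies 69 to 90 days before the end of the protocol's own 120-day period, for subjects who start new anticancer therapy. The upper figure takes cessation as the last dose; the lower one assumes it is dated one cycle later.

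The residual-drug figures rest on the stated half-life and on simple exponential decay. They show that exposure is plausible at day 30. They do not measure fetal risk, and no passage links a residual level to harm.

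The practical size is small. Few pregnancies are expected in this population, and the sample size, power and primary analysis are untouched. This is a cheap improvement to safety reporting, not a flaw in the trial's conclusions.

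**What to change.** Amend 8.2.2 so that starting new anticancer therapy does not end pregnancy and partner-pregnancy reporting before 120 days after the last dose. This means deleting the 30-day branch and the earlier-of clause.

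Keep the existing limb covering the trial and the 120 days after its completion. Replacing it with a single window counted from the last dose could shorten reporting for subjects who start no new therapy, because Section 8.1.6.1 keeps those who stop without progression in 12-weekly follow-up and their trial completion may fall well after the last dose.

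State the starting point of each period: last dose, cessation of treatment, or completion of the trial. Say whether survival follow-up counts as part of the trial.

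Reconcile 6.4.1, 6.4.2 and 8.2.2, and correct the references to 7.2.2. How long contraception should last is for the sponsor and investigators to confirm; this point does not choose a duration.

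The cost is a wording amendment. Twelve-weekly survival calls already continue after new therapy starts, so contact exists. The small downside is that some reported pregnancies will also have been exposed to the later treatment, which can be recorded with the report.
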